#### **2.2.2.4. Extent of Exposure**

Treatment duration is defined as the amount of elapsed time between the first and the last day that study medication was taken (inclusive). It will be calculated (in days) in terms of the

difference in relative study days between the last and first dose of study medication, plus one day. If the end date of the medication intake is unknown for subjects who either completed or early terminated the study (eg, subject is lost to follow-up), it will be imputed as the earlier of the disposition date (ie, date of the last contact with subject) and 14 days from the date that the last medication kit is dispensed if the last contact visit is either V1E (OL baseline), V2E (W2), V3E (W4) , or V4E (W6), and 28 days from the date that the last medication kit is dispensed is V5E (W8) or after.

Descriptive statistics (N, mean, standard deviation, median, and range) will be presented by analysis group and analysis subgroup for treatment duration. Number of subjects with duration in each of following categories (days):  $\geq 14$ ,  $\geq 28$ ,  $\geq 56$ ,  $\geq 84$ ,  $\geq 112$ ,  $\geq 140$ ,  $\geq 168$ ,  $\geq 196$ ,  $\geq 252$ ,  $\geq 308$ , and  $\geq 364$ ; 1-13, 14-27, 28-55, 56-83, 84-111, 112-139, 140-167, 168-195, 196-251, 252-307, 308-363,  $\geq 364$  days will also be presented. Return of the blister card at any given visit is not a prerequisite for inclusion in exposure summary statistics if corresponding dose start and end dates are reported.

## **2.2.2.5. Study Medication and Prior and Concomitant Medications**

### **2.2.2.5.1. Study Medication**

Descriptive summary statistics (N, mean, median) for the mean daily dose will be provided by analysis group and analysis subgroup, respectively, at each post-baseline visit, in the first 52-weeks treatment period, and overall treatment period. In addition, frequency distribution of the following dose information will be summarized:

- dispensed dose by study visit.
- predominant dose in the first 52-weeks treatment period, and during the open-label treatment period, respectively.

Return of the blister card at any given visit is not a prerequisite for inclusion in average daily dose summary statistics or predominant dose summary statistics if corresponding dose start and end dates and amount are reported.

### **2.2.2.5.2. Concomitant Medications**

Concomitant medications during the open-label treatment period (see [Section 2.1.2](#)) (ie, medications taken during the OL treatment period) are coded using World Health Organization (WHO) Drug Dictionary and Anatomical Therapeutic Chemical (ATC) codes.

Number and percentage of subjects taking concomitant medications will be provided by level 3 ATC classification and preferred name by analysis group. Since medications are coded to ATC classification by indication, preferred names may appear under multiple ATC classifications. Medications started and stopped before the open-label treatment period as well as the medications started after last dose of study drug will be included in the prior and concomitant medication listing only.

### **For subjects continued from Study D1050326**

The number and percentage of subjects taking the following categories of concomitant medications will be provided:

- With Concomitant Mood Stabilizer;
- With Concomitant Antidepressant;
- With Concomitant Mood Stabilizer or Antidepressant;
- With Concomitant treatment of ADHD;
- With Concomitant treatment of ADHD continuing from core study

Mood stabilizers, antidepressants, and treatment of ADHD will be determined by medical review prior to sign-off of the SAP.

#### **2.2.2.5.3. Concomitant Use of Benzodiazepine**

The number and percentage of subjects, who received benzodiazepine medications during the open-label treatment phase, will be summarized by preferred term and analysis group, respectively.

##### **For subjects continued from Studies D1050301 and D1050326**

A conversion chart for standardizing selected benzodiazepines to an equivalent dosage of Lorazepam is provided in [Attachment 4.4](#). Specifically, for each subject, a weight value corresponding to the number of days of benzodiazepine use in a given study visit will be used for calculating the mean daily dose for each study visit; the average total daily dose during the open-label treatment phase will be calculated as the sum of the total daily dose divided by the total days of the benzodiazepine medication administration. The usages of each benzodiazepine medication, including average total daily dose and equivalent dosage to Lorazepam over time, will be provided in a listing.

#### **2.2.2.6. Psychiatric History and Medical History Prior to DB Phase of Core Study**

Psychiatric history and medical history prior to DB phase of core study will be summarized in the same way as in the core study.

### **2.3. Efficacy**

#### **2.3.1. Efficacy Analysis Specifications**

##### **2.3.1.1. Definition**

The effectiveness endpoints in this study are:

##### **For subjects continued from Study D1050301**

- Change in PANSS total, positive, negative, general psychopathology, and excitability subscale scores
- Change in the CGI-S
- Change in the PQ-LES-Q percentage maximum possible score
- Change in the CGAS total score

**For subjects continued from Study D1050325**

- Change in the ABC irritability subscale score and the other subscale scores (hyperactivity, stereotypy, inappropriate speech, and lethargy/social withdrawal)
- Change in the CGI-S
- Change in the CY-BOCS modified for pervasive developmental disorders (PDDs)
- Change in the CGSQ

**For subjects continued from Study D1050326**

- Change in the CDRS-R total score
- Change in CGI-BP-S score (depression, mania, overall bipolar illness)
- Proportion of subjects who meet symptom remission, defined as CDRS-R Total Score  $\leq 28$  and YMRS total score  $\leq 8$  and CGI-BP-S depression score  $\leq 3$  at study visit
- Change in the PARS total score
- Change in the PQ-LES-Q score
- Change in the CGAS score
- Change in the ADHD-RS total score

**2.3.1.1. Positive and Negative Syndrome Scale PANSS**

The PANSS is only applied to subjects who continued from Study D1050301.

The PANSS is comprised of 30 items and three scales:

- the Positive scale contains seven questions to assess delusions, conceptual disorganization, hallucinations behavior, excitement, grandiosity, suspiciousness /persecution, and hostility; Positive subscale (range 7-49) is calculated as sum of Items P1 to P7 in the positive subscale;
- the Negative scale contains seven questions to assess blunted effect, emotional withdrawal, poor rapport, passive/apathetic social withdrawal, lack of motivation, and

similar symptoms; Negative subscale (range 7-49) is calculated as sum of Items N1 to N7 in the negative subscale;

- the General Psychopathology subscale addresses other symptoms such as anxiety, somatic concern, and disorientation; General psychopathology subscale (range 16-112) is calculated as sum of Items G1 to G16 in the general psychopathology subscale.

An anchored Likert scale from 1-7, where values of 2 and above indicate the presence of progressively more severe symptoms, is used to score each item. Individual items are then summed to determine scores for the three scales, as well as a total score. As a result, the total score may range from 30 to 210, positive and negative sub-scores may range from 7 to 49, and the general psychopathology sub-scores may range from 16 to 112. In addition, a subscale of excitability will be derived, which consists of the following four items from the PANSS: excitement, hostility, uncooperativeness, and poor impulse control. The sum of the four items ranges from 4 to 28.

In general, higher values of PANSS scores represent greater severity of illness. If one or more items are missing, no imputation will be performed and the total score and the scores of the subscales that include these items will be left missing.

#### **2.3.1.1.2. Clinical Global Impression – Severity**

The CGI-S is applied to subjects who continued from Study D1050301 and Study D1050325. The CGI-S is a single value, clinician-rated assessment of illness severity, and 7-point scale with range from 1='Normal, not at all ill' to 7='Among the most extremely ill patients'. A higher score is associated with greater illness severity.

#### **2.3.1.1.3. Quality of Life Enjoyment and Satisfaction Questionnaire (Pediatric Q-LES-Q)**

The Pediatric Q-LES-Q is applied to subjects who continued from Study D1050301 and Study D1050326.

The Pediatric Q-LES-Q is a 15-item self-report measure of the degree of enjoyment and satisfaction in various areas of daily living, based on the content of the Short Form of the Q-LES-Q. Each item is rated on a 5-point scale, ranging from 1 (very poor) to 5 (very good). The first 14 items are the same as the General Activities section of the regular Q-LES-Q form and are used to compute the raw score. The PQ-LES-Q-SF percentage maximum possible score is calculated as follows:

$$\% \text{ Max} = 100 \times (\text{Raw Score} - \text{Minimum Score}) / (\text{Maximum Score} - \text{Minimum Score}),$$
 where the Minimum Score equals 14 and the Maximum Score equals 70, and the % maximum possible score can range from 0% to 100%. Higher scores indicate better quality of life.

#### **2.3.1.1.4. Clinician- rated Children’s Global Assessment Scale (CGAS)**

The CGAS is applied to subjects who continued from Study D1050301 and Study D1050326.

The Children’s Global Assessment Scale (CGAS) is a numeric scale (1 through 100) used by mental health clinicians to rate the general functioning of children under the age of 18, where 1 represents the most impaired functioning and 100, superior functioning. Each decile (e.g., 1–10, 11–20) has a descriptive header (e.g., “Moderate impairment in functioning in most domains”) and examples of behaviors and types of environmental accommodations that might be seen at that level of functioning. Scores above 70 on the CGAS indicate functioning within the range of typically developing children of the same age as the child being rated while scores below 60 indicate a definite clinical case.

#### **2.3.1.1.5. Children’s Depression Rating Scale, Revised (CDRS-R)**

The CDRS-R is only applied to subjects who continued from Study D1050326.

The CDRS-R is a semi-structured, clinician-rated instrument designed for use with children and adolescents between the ages of 6-17 years. It contains 17 ordinally-scaled items that evaluate the presence and severity of symptoms commonly associated with depression in childhood. The CDRS-R is administered separately to the patient and to the caregiver; among 17 items, 14 items are based on separate interviews with child and parent, 3 items are based solely on the rater’s observation of child (ie, no questions). The 14 items (see below) are rated on a 1 (no psychopathology) to 7 (most psychopathology) scale, where a rating of 3 represents mild psychopathology. The 3 items (sleep disturbance, appetite disturbance, listless speech) are rated on a 1 (no pathology) to 5 (most pathology) scale.

1) Impaired Schoolwork	8) Irritability
2) Difficulty Having Fun	9) Excessive Guilt
3) Social Withdrawal	10) Low Self-Esteem
4) Sleep Disturbance	11) Depressed Feelings
5) Appetite Disturbance	12) Morbid Ideation
6) Excessive Fatigue	13) Suicidal Ideation
7) Physical Complaints	14) Excessive Weeping

The CDRS-R total score ranges from 17-113. In general, higher values of CDRS-R total score represent greater severity of illness

#### **2.3.1.1.6. Clinical Global Impression-Bipolar Version, Severity of Illness (CGI-BP-S)**

The CGI-BP-S is only applied to subjects who continued from Study D1050326.

The CGI-BP-S is a three-question clinician-rated assessment of the subject’s current illness state (depression, mania, and overall) using a 7-point scale (1(normal, not ill) to 7 (very severely ill)) for each question, where a higher score is associated with greater illness severity.

### **2.3.1.1.7. Pediatric Anxiety Rating Scale (PARS)**

The PARS is only applied to subjects who continued from Study D1050326.

The PARS is a clinician-rated instrument for assessing over time the severity of anxiety symptoms associated with common DSM-IV anxiety disorders (generalized anxiety disorder, separation anxiety, and social phobia) in children ages 6-17 years. The PARS is administered separately to the subject and to the caregiver. The instrument has 2 sections. The first section includes a 50-item symptom checklist, which the clinician rates as present or absent during the past week. The second section is comprised of 7 severity impairment items reflecting the severity/impairment of all symptoms endorsed in Section 1 of the PARS (during the past week). Each question is answered on a 0-5 Likert scale (0 for none, and 1-5 for minimal to extreme) with alternative responses of 8=Not Applicable and 9=Does Not Know. Scores of 8 or 9 are not counted in the summation as per the PARS instructions. The PARS total score over all 7 questions ranges in value from 0 to 35.

### **2.3.1.1.8. Attention-Deficit/ Hyperactivity Disorder Rating Scale (ADHD-RS)**

The ADHD-RS IV is only applied to subjects who continued from Study D1050326.

The ADHD-RS IV is a validated scale that measures the behaviors of children with ADHD. The ADHD-RS IV consists of 18 items reflecting current symptomatology of ADHD based on DSM-IV-TR criteria. Each item is scored from a range of 0 (no symptoms) to 3 (severe symptoms) with total scores ranging from 0 to 54. The 18 items may be grouped into two sub-scales: hyperactivity/impulsivity (even number items 2 through 18) and inattentiveness (odd number items 1 through 17), ranging from 0 to 27.

## **2.3.1.2. Analysis Methods**

No inferential statistics on effectiveness will be presented. For all of the continuous effectiveness assessments, descriptive summary statistics (N, mean, standard deviation, median, range, and a 95% confidence interval) will be presented by analysis subgroup, at DB baseline, OL baseline, each of post-OL visit, Week 52 LOCF, and the endpoint in the open-label study. All analyses for the scheduled assessments will be based on observed cases (OC). In addition, for all effectiveness evaluations, changes from DB baseline and OL baseline will be presented in a similar way using summary statistics, as described above.

### **For subjects continued from study D1050301**

At a visit in extension study, responders relative to DB Baseline are defined as those who show a 20% or more reduction (i.e., improvement) from baseline in the PANSS total score from DB Baseline. The percent change of PANSS total score relative to DB Baseline is defined as  $[100 * \text{Change from DB Baseline} / (\text{DB Baseline} - 30)]$  since 30 is the lowest possible value for PANSS. At a post-OL Baseline visit, responders relative to OL Baseline are defined as those

who show a 20% or more reduction (i.e., improvement) from OL Baseline. The percent change of PANSS total score relative to OL Baseline is defined as [100\*Change from OL Baseline/(OL Baseline – 30)].

#### **For subjects continued from study D1050325**

At a visit in extension study, responders relative to DB Baseline are defined as those who show a 25% or more reduction (i.e., improvement) from baseline in the ABC irritability subscale score from DB Baseline. The percent change of ABC irritability subscale score relative to DB Baseline is defined as [100\*Change from DB Baseline/(DB Baseline)]. At a post-OL Baseline visit, responders relative to OL Baseline are defined as those who show a 25% or more reduction (i.e., improvement) from OL Baseline. The percent change of ABC irritability score relative to OL Baseline is defined as [100\*Change from OL Baseline/(OL Baseline)].

#### **For subjects continued from study D1050326**

At a visit in extension study, responders relative to DB Baseline are defined as those who show a 50% or more reduction (i.e., improvement) from DB Baseline in CDRS-R total score. The percent change of CDRS-R total score relative to DB Baseline is defined as [100\*Change from DB Baseline/(DB Baseline – 17)] since 17 is the lowest possible value for CDRS-R total score; At a post-OL Baseline visit, responders relative to OL Baseline are defined as those who show a 50% or more reduction (i.e., improvement) from OL Baseline. The percent change of CDRS-R total score relative to OL Baseline is defined as [100\*Change from OL Baseline/(OL Baseline – 17)].

Frequencies and percentages of CDRS-R responders relative to both DB Baseline and OL Baseline over time will be reported by analysis subgroup, respectively. Frequencies and proportions of remitters as well as the corresponding 95% Clopper-Pearson (ie, exact) CI of the proportion at DB baseline, OL baseline, each of post-OL visit, Week 52 LOCF, and endpoint will be reported by analysis subgroup.

Subgroup analyses for CDRS-R total score and CGI-BP-S depression score will be conducted on observed values and changes from DB baseline and OL baseline by study visit, W52 LOCF, and endpoint by analysis subgroup, to examine the effects of geographic region (US, non-US) in a similar approach as described above.

### **2.4. Pharmacokinetics (PK) Analysis**

Not applicable.

### **2.5. Multiplicity Adjustment**

Not applicable.

## **2.6. Safety**

### **2.6.1. Analysis Specifications**

All safety analyses and summaries will be based on the safety analysis population. Subgroup analysis per age group may be conducted as needed.

There will be no imputation of missing values for clinical laboratory test results, vital sign measurements, and ECG evaluations in the by-visit analyses.

### **2.6.2. Age Over Time**

Descriptive statistics (N, mean, SD, median, and range) of age will be provided by analysis group at DB screening, OL baseline, and endpoint by analysis group. Shifts from DB screening to endpoint and from OL Baseline to endpoint in age group (years) below will be produced by analysis group to show the percentage of subjects within the age categories:

- Age group 2: 6-9 years, 10-12 years, 13-15 years, 16-17, 18-20 years.

### **2.6.3. Definition of Treatment-Emergent Occurrences in Open-Label Extension Study**

Definition of treatment-emergent adverse event is provided in [Section 2.6.4](#). Treatment-emergent occurrences of adverse reactions, including Potentially Markedly Abnormal Laboratory Values (PMALV), Potentially Markedly Abnormal Vital Signs (PMAVS), and abnormal ECG values, are defined as the assessment values that meet specific safety criteria within the open-label treatment phase (see [Section 2.1.2](#)).

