#### **2.1.2. Definition of Open-Label Treatment Phase in Extension Study**

The day of the 1st dose date in the extension study will be denoted as study Day 1. All measurements at each visit will be assigned a study day relative to this date. All data collected on/after Day 1 for subjects previously randomized to placebo group in core study or on/after the extension baseline visit for subjects previously randomized to lurasidone groups up to Week 104, including the End-of-treatment/Early Withdrawal visit, will be considered within the open-label treatment phase. That is to say, the start of the open-label treatment period is defined as Day 1 for subjects previously randomized to placebo group and the OL Baseline visit date for subjects previously randomized to lurasidone groups; the end of the open-label treatment phase is defined as the maximum of the last date of administration of study medication and the withdrawal/completion date for subjects who have completed the study.

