### **2.6.4. Adverse Events**

A treatment-emergent adverse event (TEAE) is defined as an AE onset on or after the start of open-label treatment period through 7 days after study drug discontinuation (14 days for serious adverse events and deaths). For sake of simplicity, hereafter TEAE is referred as AE in the section.

The overall incidence (ie, number and percent of subjects with one or more AE in each category) of AEs, serious AEs, deaths, AEs leading to discontinuation, drug-related AEs, serious drug-related AEs, drug-related AEs leading to discontinuation, serious AEs leading to discontinuation, and serious drug-related AEs will be summarized by analysis group and by analysis subgroup, separately.

AEs by system organ class (SOC) (number and proportion of subjects with one or more AEs within a system organ class) will be summarized by analysis group. For each AE, the percentage of subjects who experienced at least one occurrence of the given event will be provided by preferred term, grouped by system organ class, and presented by analysis group and by analysis subgroup. AEs for age subgroup summary will be also presented by SOC and preferred term and by analysis group and analysis subgroup.

Furthermore, additional summaries will be created based on the following combined preferred terms:

- Dystonia - preferred terms: dystonia, trismus, oculogyric crisis, oromandibular dystonia, tongue spasm, torticollis
- Parkinsonism - preferred terms: bradykinesia, drooling, extrapyramidal disorder, glabellar reflex abnormal, hypokinesia, parkinsonism, psychomotor retardation
- Somnolence - preferred terms: hypersomnia, sedation, somnolence, hypersomnolence

According to MedDRA coding guidelines for Lurasidone pediatric program,

- EPS-related reported terms for Tremor, Rigidity or Muscle Rigidity will be queried for further specificity. Sites will qualify if the reported term is Parkinsonian or non-Parkinsonian in nature; if confirmed, the reported term will be coded to lowest level terms of Parkinsonism; if not, the term will be coded to specific symptom.
- For reported term Restlessness, sites will qualify if the reported term is Akathisia or non-Akathisia in nature; if confirmed, the reported term will be coded to lowest level terms of Akathisia; if not, the term will be coded to specific symptom.

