The normal reference ranges for laboratory tests will be used to determine whether the laboratory test value is below, within, or above the normal range. Shifts from DB baseline and shifts from OL baseline over time will be produced by analysis group to show the percentage of subjects with laboratory test values below, within, and above the normal range.

Potentially Markedly Abnormal Laboratory Values (PMALV) per conventional unit and the equivalent International System of Units (SI) for selected laboratory parameters can be found in Table 3.1. The criterion of PMALV is satisfied if a value falls into the potentially markedly abnormal range. The number and percentage of subjects with treatment emergent PMALV in the first 52-weeks treatment period and during overall treatment period, and the number and percentage of subjects who meet the threshold in [Table 3.2](#) per conventional unit and the equivalent International System of Units (SI) by study visit will be presented by analysis group and by analysis subgroup as needed.

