**Table 4 QTc Prolongation for Pediatric and Adolescent Subjects**

QTc Prolongation
QTc >460 msec
QTc >480 msec
QTc >500 msec
Increase from OL baseline QTc $\geq$ 30 msec
Increase from DB baseline QTc $\geq$ 30 msec
Increase from OL baseline QTc $\geq$ 60 msec
Increase from DB baseline QTc $\geq$ 60 msec

The number and percentage of subjects having a QTc prolongation using Fridericia correction method for DB baseline, OL baseline, post-OL baseline visit, W52 endpoint, endpoint, and any treatment emergent occurrence in the first 52-weeks treatment period, and during the open-label treatment period (the worst case), will be summarized by analysis group. A listing of ECG data for subjects with at least one prolonged QTc will also be produced.

For other ECG parameters, subjects will be classified as normal or abnormal using the limits specified in Table 5. For abnormal ECG parameter reporting, counts and percentages of subjects will be presented for DB baseline, OL baseline, each post-OL baseline visit, W52 endpoint, endpoint, and any treatment emergent occurrence in the first 52-weeks treatment period, and during the open-label treatment phase by analysis group.

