**Table 6.2 Weight Status Categories for Pediatric and Adolescent Subjects per CDC Standard**

BMI (kg/m  )	Weight Status
< 5 th percentile	Underweight
5 th percentile ≤ BMI ≤ 85 th percentile	Normal
85 th percentile < BMI ≤ 95 th percentile	Overweight
>95 th percentile	Obese

Shifts from OL baseline and shifts from DB baseline over time for weight status categories (Tables 6.1) will be summarized by analysis group to show the number and percentage of subjects that fall into above categories. A similar shift analysis will be done for US subjects (Table 6.2) by analysis subgroup D.

The number and percentage of subjects with Potentially Markedly Abnormal Vital Signs (PMAVS), defined in [Table 7](#), will be presented by analysis group at DB baseline and OL baseline (when applicable), post-OL baseline visits, W52 endpoint, endpoint, and in the first 52-weeks treatment period, and any treatment-emergent occurrence during the open-label treatment phase (the worst case).

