**Table 10.1 Comparative Endpoint Relative to DB Baseline**

Comparative Endpoints	Analysis Time Points Involved	Derivation Rule
Emergence of Suicidal Ideation	DB Baseline(a) Any extension visit(b)	No suicidal ideation at DB Baseline, and any type of suicidal ideation in 'any extension visit'
Emergence of Serious Suicidal Ideation		No suicidal ideation at DB Baseline, and any serious suicidal ideation [ideation score of 4 or 5] in 'any extension visit'

Emergence of Suicidal Behavior		No suicidal behavior at DB Baseline, and any type of suicidal behavior in 'any extension visit'	
Emergence of Suicidality		No suicidality at DB Baseline, and any suicidality in 'any extension visit'	
Worsening of Suicidal Ideation		Most severe suicidal ideation in 'any extension visit' is more severe than the most severe value at DB Baseline	
(a): Definition of DB Baseline: see Table 9 in D1050301 SAP, and Table 9 in D1050326 SAP ;			
(b): see Table 9.			

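### SAP 2.6.3 labels laboratory, ECG and orthostatic findings treatment-emergent without requiring that they were absent at baseline (39 of 47 criteria), and for prior-placebo subjects its date rule can admit a pre-lurasidone value

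*SAP*

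**What the plan says.** SAP 2.6.3 covers potentially markedly abnormal laboratory values (PMALV), potentially markedly abnormal vital signs (PMAVS) and abnormal ECG values. Treatment-emergent occurrences of these "are defined as the assessment values that meet specific safety criteria within the open-label treatment phase".

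The reporting sections use that label:

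- **Laboratory (2.6.5).** "The criterion of PMALV is satisfied if a value falls into the potentially markedly abnormal range". The planned output is "The number and percentage of subjects with treatment emergent PMALV in the first 52-weeks treatment period and during overall treatment period".
- **ECG (2.6.6).** QTc prolongation is to be shown for "any treatment emergent occurrence in the first 52-weeks treatment period, and during the open-label treatment period (the worst case"). The Table 5 limits for HR, PR and QRS are handled in the same way.
- **Vital signs (2.6.7).** The Table 7 criteria are to be shown for "any treatment-emergent occurrence during the open-label treatment phase (the worst case").

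The window is set in SAP 2.1.2. For prior-placebo subjects it takes in "All data collected on/after Day 1 for subjects previously randomized to placebo group in core study", where Day 1 is the date of the first extension dose. For prior-lurasidone subjects it starts at the OL Baseline visit.

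**The concern.** Treatment-emergent normally means new or worse on treatment, and the SAP mostly uses it so. An adverse event must start in the phase: "A treatment-emergent adverse event (TEAE) is defined as an AE onset on or after the start of open-label treatment period". C-SSRS emergence in Table 10.1 needs "No suicidal ideation at DB Baseline, and any type of suicidal ideation in" any extension visit. The UKU rules in 2.6.12 need a first occurrence or a worsening. In the laboratory, ECG and orthostatic tables the same label would mean only that the finding was present. A subject who met a limit before any study drug and still meets it would be counted.

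A second gap concerns prior-placebo subjects. The mania rule in SAP 2.6.4 leaves out their visits with study day 1 or earlier; 2.6.3 has no such exclusion.

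At stake is the reading of long-term pediatric safety rows. A reader of the study report would take them as abnormalities that arose on lurasidone, and no planned summary table would show how many did.

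**Working it through.** **1. Which criteria lack a baseline condition.** Counting one per parameter in Tables 3.1, 5 and 7 and one per row in Table 4:

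| Source | No baseline condition | Change from baseline built in |
|---|---|---|
| Table 3.1 (PMALV) | 7 hematology + 17 chemistry + 4 lipid + 2 urinalysis = 30 | 0 |
| Table 4 (QTc) | 3 (>460, >480, >500 msec) | 4 (increases from OL or DB baseline) |
| Table 5 (HR, PR, QRS) | 3 | 0 |
| Table 7 (PMAVS) | 3 (orthostatic SBP, DBP, pulse) | 4 (SBP, DBP, pulse, temperature) |
| Sum | 39 | 8 |

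39/47 = 83.0%. Other ways of counting change little: 40/48 = 83.3% with fasting and random glucose split; 53/64 = 82.8% with each low and high bound counted; 39/51 = 76.5% with the four change-based vital-sign rows counted once per baseline.

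**2. The Day 1 value in prior-placebo subjects.**

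- Protocol 11.4.1 puts Visit 1E on the same day as the core study's final visit.
- SAP 2.1.5 takes OL Baseline from that core visit and defines it as the last assessment on or before Day 1.
- Protocol 10.6 has dosing in the evening.
- SAP 2.1.2 opens the window by date, not by time.

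If the first dose is taken on the visit date, OL Baseline precedes all lurasidone yet lies inside the window. Each such prior-placebo subject who meets a limit at OL Baseline is then counted, even if every later value is normal. If the first dose is a day later, the value falls outside. The gap can also reach the criteria that measure change from DB baseline.

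**3. Effect on count and percentage.** The documents give no baseline prevalence, so the inputs are assumed. Suppose the Day 1 value has been excluded. Let N be all subjects, B those meeting the criterion at the reference baseline, k those in B who meet it again in the open-label phase, and m the new-onset subjects.

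- Present rate: (k + m)/N
- New-onset rate among subjects at risk: m/(N - B)

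The present count exceeds the new-onset count by k, which is never negative. As k/N, in percentage points, with enrolled numbers from SAP 1.2.1 as N:

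| Assumed k | From D1050301 (271) | From D1050325 (125) | From D1050326 (306) | All (702) |
|---|---|---|---|---|
| 0 | 0 | 0 | 0 | 0 |
| 1 | 0.37 | 0.80 | 0.33 | 0.14 |
| 5 | 1.85 | 4.00 | 1.63 | 0.71 |
| 10 | 3.69 | 8.00 | 3.27 | 1.42 |

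The two percentages differ in a direction that depends on k/B against m/(N - B). Assume N = 271, B = 20, m = 10, so the at-risk rate is 10/251 = 3.98%:

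- k = 0: present rate 10/271 = 3.69%, lower than 3.98%
- k = 1: 11/271 = 4.06%, slightly higher
- k = 10: 20/271 = 7.38%, clearly higher

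**4. What is already planned.**

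- Counts at each baseline for ECG and PMAVS (2.6.6, 2.6.7)
- An any-visit count for the double-blind period (2.1.7)
- By-visit counts at the Table 3.2 thresholds for prolactin and three lipids
- Laboratory shifts against the normal range (2.6.5) and central-read ECG shifts (2.6.6)
- Subject listings

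The counts are marginal and do not link a subject's baseline to later values. The shifts do link them, but against other limits and not as an any-visit count. The listings allow reconstruction subject by subject. None tabulates any-visit new onset against the 39 criteria.

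**The case against.** The strongest reply is that 2.6.3 defines its term openly and that 2.1.7, 2.6.6 and 2.6.7 call these analyses worst case. The SAP is not uniform either: the YMRS part of treatment-emergent mania in 2.6.4 is an absolute score with no requirement that it was absent at baseline. That stands, so a reader should not infer that 2.6.3 is the SAP's only departure from new onset. But worst case says which value is taken, not whether it is new, and the rows still carry the treatment-emergent label.

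A pure new-onset count has losses of its own. It drops a subject whose existing abnormality worsens. If DB baseline were the only reference, it would also drop a prior-placebo subject who was abnormal at DB baseline, normal at OL Baseline and abnormal again on lurasidone. Both points stand and shape the remedy.

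On Day 1, the separate start points in 2.1.2 suggest that the pre-dose visit of prior-placebo subjects was meant to be left out. That is likely, but the date rule does not secure it. ECG and PMAVS counts are specified by analysis group, so prior-placebo subjects need not be shown apart, although 2.1.9 allows subgroup presentation as needed.

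**Conclusion.** The point holds as a fault of labelling and definition worth fixing before the full study report. As written, 39 of 47 criteria can be counted as treatment-emergent when the finding was already there. For prior-placebo subjects dosed on the visit date, a value from before any lurasidone can be counted.

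Three stronger readings are tempting and not supported:

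- **That the printed percentages are inflated.** Only the count has a fixed direction. The size is unknown, and the excess is zero if no one meets a criterion at baseline.
- **That every extra subject is unrelated to lurasidone.** Subjects abnormal at DB baseline can include some whose abnormality resolved and returned on drug.
- **That the main safety results are affected.** Protocol 14.4.1 makes adverse events, serious adverse events and discontinuations due to adverse events primary. These tables are secondary and descriptive, with no tests.

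Counting the OL Baseline value for prior-lurasidone subjects is not in question, since it was taken on drug. The Day 1 part rests on the first dose and the core final visit sharing a date. How often they do is not stated.

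**What to change.** 1. **Day 1.** For prior-placebo subjects, exclude assessments with study day 1 or earlier from all treatment-emergent laboratory, ECG and vital-sign counts, as 2.6.4 already does for mania. Leave the window for prior-lurasidone subjects unchanged.
2. **Label.** Rename the present count *any abnormal value during the OL phase (worst case)* and keep it. Worsening and recurrence then stay visible, and results remain comparable with the report from final database lock 1.
3. **New onset.** Beside it, for the 39 criteria, count subjects who did not meet the criterion at the reference baseline and met it later. The denominator is subjects with a non-missing reference baseline not meeting the criterion and at least one later value. The reference is the last value before lurasidone: DB baseline for prior-lurasidone subjects, OL Baseline for prior-placebo subjects. Treat low and high limits separately, and report missing baselines apart, because 2.1.14.1 does not impute OL Baseline.

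**Cost.** SAP wording, one flag per criterion and extra rows. With one reference per subject and two periods (first 52 weeks, overall) this is 39 x 2 = 78 counts per table column, or 53 x 2 = 106 with every bound separate. Both baselines are already held (SAP 2.1.5), and SAP section 1 places lock 2 in the future. The full report will need a footnote explaining why its figures for subjects from D1050301 differ from the completed schizophrenia report.
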